8.6 Limitations

Technical limitations of the system will affect the generalisability of results. At present, patients without access to any digital device would not be able to use the products and are therefore not eligible for inclusion in the study.

As Wysa's algorithm is currently only compatible with the English language, non-English speaking patients will be excluded from the study, also limiting the representativeness of the sample.

8.7 Generalisability

Limitations to the generalisability of the study results were noted in the previous section. However, it is expected that the results will be generalisable to most individuals seeking general mental health support. We will also make efforts to recruit a representative sample of the UK population.

9 ETHICAL AND REGULATORY CONSIDERATIONS

9.1 Assessment and Management of Risk and Other Ethical Issues

Standard ethical issues will be managed as follows:

- Recruitment: Participant eligibility will be determined by the screening process they undergo upon referral to NHS talking therapies. Everyone who enters the NHS talking therapies pathway and meets eligibility criteria and consents will be eligible for the study.
- All participants will be included in the quantitative analyses, thus avoiding recruitment bias.
- Power relations and other potential biases: Pre-established inclusion and exclusion criteria will be used to avoid any potential bias from the researchers as well as any coercion from participants. To prevent participation bias, only participants who would not otherwise progress down the standard care pathway will be excluded.
- Confidentiality: To control any potential perceived issues in this area, participant confidentiality will be protected using data protection procedures that are compliant with the Data Protection Act 2018 (DPA 2018).
- Study Governance: To maintain the integrity of the study and avoid any commercial influence, a research contract will be established between Wysa and the NHS talking therapies service that will ensure the independence of study design and execution and the unrestricted right to publish all results.
- A comprehensive risk register and Hazard log is maintained by Wysa across its development as part of its Clinical Safety Management file. This risk register will be regularly reviewed and updated as part of the project management governance. Key risks for this project include:
 - Clinical: A Structured What-IF Technique (SWIFT) analysis has been completed which highlighted that the main clinical risk of this project is unintended harm. This could be psychological or physical risk caused by unintended increase in psychological distress. We have mitigated the risk to patients by building a clinically underpinned crisis response pathway, with handover capabilities to the clinical team for the intervention (cCBT) element of the study.
 - Excessive screen time: Health risks associated with excessive screen time are mitigated by ensuring that many of the strategies and skills taught by the app encourage users to complete them away from the screen. All risks and mitigations are outlined in the clinical safety management file.
 - Commercial: The need for good quality evidence combined with long sales cycle times in healthcare can produce a risk of limited cash flow - this is mitigated by Wysa's maturity as a company and track record of securing investment funding as needed. As a real-world use study the evidence generated by the project will help to respond to commissioners' need for a high quality evidence base, removing a core barrier to implementation.

9.2 Research Ethics Approval

The study protocol will undergo institutional and regulatory review and approval prior to commencement. To ensure that our data reporting is in line with NHS standards we will be following the Department of Health and Social Cares guidelines for good practice for digital and data driven health technologies [19]. As per the guidelines, we will be applying the Caldicott Principles for the collection and evaluation of patient data

Ethical approval is being sought from the Health Research Authority and the relevant Research Ethics Committee with this submission [20.

Wysa, as the study sponsor, will ensure that the study has received ethics approval from a research ethics committee (REC) and has received Health Research Authority (HRA) approval.

9.3 Peer Review

The study will undergo peer review and ethical approval via the NHS Trusts involved.

9.4 Patient and Public Involvement

PPI representatives played an important part in our testing process prior to release of the electronic triage and the Wysa cCBT programmes. A number of our PPI groups have previously been involved in the review of academic articles, the development of public facing content, and the presentation of findings at conferences and we plan to continue this during this project.

Payments are made in recognition of members' time based on NIHR Involve guidance on payment of fees and expenses [21]. Travel expenses are reimbursed in accordance with this policy together with other expenses and travel costs.

9.5 Protocol Compliance

Regular meetings will be held between the sponsor (Wysa) and the clinical services to ensure that the protocol is being followed. Should there be a serious breach of the safety or physical or mental integrity of the participants the Sponsor will notify the licensing authority in writing.

9.6 Consent

Service consent mechanisms will be adopted as well as consent via the Wysa App. As many patients are understandably concerned about how their data will be used, participants are able to ask Wysa for further details about their data and can speak with the Wysa team for further information. It will be made clear that patients have a right to withdraw from the study at any time and have their data destroyed. Declining consent will not affect patients' participation in the study or their clinical care.

9.7 Data Protection and Patient Confidentiality

The Wysa system stores patient identifiable data directly into NHS talking therapiesus electronic patient records using an API built through the Mayden Prism system. This solution complies with the General Data Protection Regulation (GDPR) and was built to meet the NHS DCB0129 safety standard and the code of conduct for the use of artificial intelligence [22]. Version number 1.1 - 25th November 2023 21

The team has specific expertise in this area as Wysa employs a qualified Clinical Safety Officer who has experience of overseeing the safe integration of solutions that share patient data into the NHS. Wysa also monitors compliance with the information governance requirements set out by the Department of Health and Social Care by using the Data Security and Protection Toolkit.

Wysa maintains a data recovery plan in case of emergency which ensures that loss of functionality does not directly impact on patient experience or safety. Wysa completes a regular internal audit of data protection and data safety as well as an annual external audit. We have clear reporting and escalation procedures in place and can provide copies of these policies as required.

A Data Protection Impact Assessment will be conducted with the organisations involved in this study, and Information Sharing Agreements will be developed in collaboration with the Data Protection Officers from Dorset University NHS Foundation Trust and Lancashire and South Cumbria NHS Foundation Trust. To mitigate patient concerns about data use, privacy, and security, these are clearly explained in the FAQ section on the App. If patients are unclear or unhappy with how their data will be protected, they will have the opportunity to refuse to consent to participate in the study without any consequences to their care. They will also be informed that they are free to withdraw their consent at any point in the study and will continue in the standard care pathway.

Interactions with the AI component of the app will create potentially identifiable patient data which will be stored as part of the medical record in Wysa's role as data processor. Patient identifiable data will not be sold to any other party and will not be shared with any organisation unless they are a partner in the study and have an appropriate information sharing agreement in place. Strict access controls will be implemented to protect this data.

Each of the study participants will be given a unique identifier. The primary key between unique ID and participant shall be stored securely for reference purposes and provided to the participant so that they can request that their data be withdrawn from the study. This can be requested at any point prior to data aggregation and will result in all of the patient's files and data being destroyed. Data collected in the study will be analysed using the unique identifiers rather than patient names. Primary research data will be retained for 10 years following publication of the final study results. Study participants will have the option to retain their information within the WYSA app for their onward use or to reset their data at the completion of the study.

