From here the patient will be offered the opportunity to download the Wysa app as a waitlist support tool until they are offered an intervention. The Wysa app includes over 150 self care tools, conversational AI and daily check-ins and reminders via push notifications. We will analyse data collected from within the app to understand app usage and any effect use of the app may have on mental wellbeing markers during the wait period.

Patients who are then offered Wysa's cCBT by their assessing clinician will have access to diagnosis specific weekly web or app based programmes including psychoeducational videos and CBT conversational techniques, as well as periodic reviews by an NHS talking therapies clinician through a communication dashboard called the Therapist Companion, which is also fully integrated into the service EPR system. We will report on changes in clinical outcome measures and engagement metrics to understand the efficacy of these cCBT programmes.

For all patients using Wysa within the service there is a built in SOS response. Wysa has three pathways to crisis alert and response:

- Patients are able to trigger crisis help by selecting the 'SOS' button on the app.

Version number 1.1 - 25th November 2023

- Crisis response will be triggered by responses to PHQ9 question 9
- Crisis response will be triggered when risk language is used (and confirmed by the chatbot) within free text.

When Wysa or the user triggers the crisis response pathway, users will be offered to complete a safety plan, engage in grounding exercises, and be provided with local or national crisis helplines. We will collect data including the number of times that the Wysa SOS response is triggered, the number of false positives identified by the AI, and SOS tool usage.

After patients have been discharged, Wysa can also be used as a support/ relapse prevention tool. All participants will have access to the AI Chatbot and self tools for 12 months from onboarding.

[figure not shown]

Figure 1. Current NHS talking therapies care pathway flows including Wysa therapeutics.

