8.2.4.2 Secondary Outcomes

There will be several secondary outcome measures (see Table 6). The secondary outcomes will also be measured at both part 1 and part 2: e-triage, whilst waiting for treatment, during treatment and at discharge from treatment.

Patient Engagement

User engagement with Wysa will be assessed using a combination of complementary measures. Examining time spent using a digital health intervention is not by itself a reliable measure of effective engagement, as it cannot differentiate between users who spend a long time on the app because they're positively engaged compared to those who are frustrated and struggling to use it. Therefore, measures of app usage will also include uptake and dropout rates, and digital user feedback.

Patient experience

Wysa's acceptability will be examined through user score ratings (in app) out of a maximum of 5.

Health-related quality of life

Version number 1.1 - 25th November 2023

Work and Social Adjustment Scale [17] will be used to assess quality of life. The WSAS is a reliable measure for impairment in functioning and one of the NHS talking therapies standardised questionnaires. It provides a descriptive self-assessment of the impact of mental health difficulties in 5 dimensions: work, home management, social leisure, private leisure and personal or family relationships .

Secondary Outcome	Outcome Measure
Health related Quality of life	WSAS[17]
Patient Engagement	Referral rates Dropout / discharge reason/ did not attend rates App usage data
Patient experience	Automated review questions periodically requested during general use of the tool

Table 6. Secondary Outcome Measurements

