8.3.3.2 Consent

To be accepted by the NHS talking therapies service participants need to consent to sharing of necessary data with their GP, as well as to data being stored safely and confidentially under GDPR regulations. Participants also need to consent to anonymised data being provided to NHSE, but can opt out of this if preferred.

Once the user downloads the app they are provided with information about how their data will be used together with an option to opt out. It will be made clear that patients have a right to withdraw from the study at any time and have their data removed. Declining consent will not affect patients' participation in the study or their clinical care.

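### Erasure on request takes participants out of the dropout, SOS and PHQ-9/GAD-7 results, so the Section 9.1 statement that all participants are analysed fails once anyone uses that right

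*Protocol*

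**What the plan says.** Three places in the protocol deal with what happens to data on withdrawal.

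- Section 9.7 gives each participant the key to their unique identifier "so that they can request that their data be withdrawn from the study". It adds that such a request, if made before the data are aggregated, "will result in all of the patient's files and data being destroyed".
- Section 9.6 says that "patients have a right to withdraw from the study at any time and have their data destroyed".
- Section 8.3.3.2 says nearly the same: "patients have a right to withdraw from the study at any time and have their data removed".

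An earlier paragraph of Section 9.7 also mentions withdrawing consent and carrying on in standard care, with no reference to destruction.

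On the analysis side, Section 9.1 states: "All participants will be included in the quantitative analyses, thus avoiding recruitment bias". Section 8.2.4.2 says that "measures of app usage will also include uptake and dropout rates", and Table 6 lists dropout, discharge reason and non-attendance as secondary outcomes. Section 6 says: "We will collect data including the number of times that the Wysa SOS response is triggered". Section 8.2.4.1 makes the before-after comparison of PHQ-9 and GAD-7 the primary analysis of Part 2.

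Nowhere does the protocol say that data collected up to withdrawal are kept, or that erasures are counted.

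**The concern.** Erasure reaches data that have already been collected. If someone who dropped out or triggered an SOS response then asks for erasure, the record that those outcomes are meant to count is deleted. The person disappears from the denominator as well, so the published rate gives no sign that anyone is missing.

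This differs from ordinary missing data, where the patient is still known to exist and can be bounded or imputed. It also cannot be repaired in an analysis plan, because destroyed records cannot be restored. Section 10.1 says the results will support a regulatory application, so an unexplained gap between those enrolled and those analysed would matter.

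The wording adds to the difficulty. Sections 8.3.3.2 and 9.6 can be read as making deletion part of withdrawing, and they set no time limit. Section 9.7 ties deletion to a request and closes the window at data aggregation, an event the protocol does not date.

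**Working it through.** **Step 1: the texts side by side.** Section 9.7 destroys everything held on a participant who asks in time. Section 9.1 says, without exception, that every participant enters the quantitative analyses. With no erasures both can be true. With one erasure they cannot. This step needs no assumed rate.

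**Step 2: inputs for an illustration.** N = 100 is the minimum sample in Section 8.3.2.1. That section gives no significance level, power, effect size or dropout rate, so the 100 cannot be reproduced, and nothing here depends on it. Everything else is assumed: D = 30 true dropouts, E participants erased, and d of those E being dropouts.

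**Step 3: dropout.** True rate = D/N = 30/100 = 30%. Reported rate = (D − d)/(N − E). If all those erased are dropouts (d = E):

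| Erased | Share of the 30 dropouts | Reported dropout |
|---|---|---|
| 1 | 3.3% | 29/99 = 29.3% |
| 2 | 6.7% | 28/98 = 28.6% |
| 5 | 16.7% | 25/95 = 26.3% |
| 10 | 33.3% | 20/90 = 22.2% |

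The direction depends on who asks. If 10 are erased and 3 of them are dropouts, the same share as in the whole sample, the rate is 27/90 = 30.0% and there is no bias. If none of the 10 is a dropout, it is 30/90 = 33.3%, which counts against Wysa.

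**Step 4: PHQ-9 (the same reasoning applies to GAD-7).** Assume those retained improve by 5.0 points and those erased by 0. The true mean is ((100 − E) × 5.0 + E × 0)/100, which is 4.95, 4.90, 4.75 or 4.50 for E = 1, 2, 5 or 10. The reported mean is 5.0 each time, an overstatement of 0.05, 0.10, 0.25 or 0.50 points. If those erased also improved by 5.0, the bias is nil.

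**Step 5: SOS.** Assume 10% of those retained and 30% of those erased trigger a response. The true rate is ((100 − E) × 10% + E × 30%)/100, which is 10.2%, 10.4%, 11% or 12% for the same E. The reported rate is 10%.

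**Step 6: with a count kept.** In the Step 3 table, if the erased dropouts are counted and all enrolled form the denominator, the rate is 30/100 = 30% for every E.

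**The case against.** Four stronger readings are tempting, and the protocol does not support them.

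- *Everyone who leaves vanishes.* Section 9.7 attaches destruction to a request. Someone who stops opening the app, misses appointments or is discharged, and makes no request, stays in the data and is counted as a dropout.
- *The bias always favours Wysa.* Sections 9.6 and 9.7 link patients' worries to data use and privacy. Requests made for that reason need not go with poor outcomes.
- *Erasure falls on app users and spares the comparison group.* The opt-out in Section 8.3.3.2 does appear at app download, and Section 8.2.1 describes participants as Wysa users. But Section 8.3.2.2 takes all accepted patients into Part 1, Section 9.7 gives the identifier to every participant, and Section 9.6 adds service consent mechanisms. The point is unsettled.
- *Nothing could ever be recovered.* Section 9.11 keeps consent records for ten years, so a bare number, consented minus analysed, may be obtainable. The protocol does not say so, and that number would not restore stage, reason, SOS status or scores.

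Three further points can be made for the plan. The Section 9.1 sentence sits under recruitment and does not define an analysis set. This is true, and it makes the conflict one of wording, but the sentence has no exception. Participant-flow counts often belong in an analysis plan. That is fair for reporting, but the decision to destroy records is made here. Lastly, an early leaver may have no later score, so erasure may add little to ordinary missingness in the before-after comparison. That also stands, and the figures in Step 4 apply only where a later score existed.

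**Conclusion.** The point holds for participants who ask for erasure before aggregation, and for them only. As written, the plan removes them from the dropout, SOS and PHQ-9/GAD-7 results, makes no provision to count them, and contradicts Section 9.1 as soon as the right is used. The deadlines also disagree between Sections 8.3.3.2 and 9.6 on one side and Section 9.7 on the other.

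How much it matters numerically is unknown. One or two erasures among 30 dropouts per 100 would move the dropout rate by about 1 percentage point (0.7 and 1.4). Ten would move it by 7.8 points. These figures assume 30 true dropouts and that all those erased are among them. Shifts in symptom change and SOS rates in Wysa's favour further require that those erased did worse than those retained, which the protocol gives no means of judging.

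This is a cheap improvement, best made before any record is destroyed. It is not a defect that invalidates the study.

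**What to change.** 1. In Sections 8.3.3.2, 9.6 and 9.7, separate two acts. Withdrawing from the study or the app leaves data already collected in the analysis under the unique identifier. Erasure happens only if the participant separately asks for it.
2. On erasure, delete the individual data but keep a non-identifying aggregate count: number erased, study part and stage. If the consent terms allow, add the reason and whether an SOS response had occurred. Disclose this in the participant information.
3. Count erased patients as withdrawals in the dropout rate, with all enrolled as the denominator. Show them as a separate line by stage, so that anyone erased after finishing can be told apart.
4. Use one erasure deadline in all three sections.
5. Reword Section 9.1 to say that all participants are analysed except those whose data were erased, with the number reported.

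The cost is an amendment to the protocol and participant information, and a tally. The downside is small but real: the promise to destroy everything is narrowed by the retained count, so the consent wording has to change, and the reported dropout rate may look slightly less favourable.

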9.8 Stopping Guidelines

If the chief investigator identifies any risks that have not been foreseen and mitigated against, the study will be paused while those risks are assessed. There is no maximum recruitment threshold.

9.9 Indemnity

The NHS Trust holds standard NHS Hospital Indemnity and insurance cover with NHS Resolution for NHS Trusts in England, which apply to this study.

9.11 Access to data

Patient identifiable data will not be sold to any other party and will not be shared with any organisation unless they are a partner in the study and have an appropriate information sharing Version number 1.1 - 25th November 2023 22

agreement in place. Records of consent will be kept for ten years after the publication of final study results, but no other personally identifiable information will be stored beyond the end of the study.

10 DISSEMINATION POLICY

10.1 Dissemination Strategy

Analysis of the data will be compiled into a published peer-reviewed paper. This data will also be used to support MHRA Class IIa regulatory approval and wider adoption practices.

The national framework for NHS talking therapies services outlines the referral and assessment pathway. WYSA has been designed to align with NHS talking therapies guidelines including minimum dataset requirements. Strong relationships across the AHSN network and central NHSX will be used to disseminate the results and gain support for further deployments.

Interoperability with digital systems is an important element of this real-world evaluation study. The API integration with Mayden Prism software is an important part of our current and proposed work streams, as it supports easy integration with existing systems and facilitates the incorporation of Wysa into existing care pathways. NHS talking therapiesus is currently one of two leading patient management systems for UK NHS talking therapies services, which will allow for rapid technical deployment following the results of this study.

